- Urine pregnancy test (for females of childbearing potential)

Subjects will receive a pretreatment regimen for infusion reaction prophylaxis. The regimen is as follows:

- Dexamethasone 10 mg PO 24-18 hours prior to administration of study drug.
- Acetaminophen 1000 mg PO 1 hour prior to administration of study drug.
- Either loratedine 10 mg PO or cetirizine 10 mg PO one hour prior to the administration of study drug.

In the event that dexamethasone was not administered previously, then 10 mg dexamethasone IV may be administered 1-3 hours prior to study drug administration.

Following completion of pre-dose assessments and administration of pretreatment regimen according to the appropriate timelines above, study drug will be administered by IV infusion over 30 minutes.

Subjects will remain in the clinic for up to 4 hours following completion of the 30 minutes IV infusion for PK assessment and safety follow-up. The following procedures will be conducted post-dose:

- Vital signs: 15 minutes (during infusion), 30 (+ 15) minutes (immediately post-infusion), 2 hr (±20 minutes) and 4 hr (±20 minutes) following initiation of study drug infusion.
- ECG at 30 (+15) minutes after initiation of study drug infusion.
- Blood samples for bertilimumab (PK analysis) at 30 (+15) minutes (immediately post-infusion) and 4 hours (±20 minutes) following initiation of study drug infusion.
- Recording of AEs (including post-infusion reactions, if applicable) and concomitant medications.

5.3 FOLLOW-UP PERIOD¹: VISIT 5 (DAY 35), VISIT 6 (DAY 42), VISIT 7 (DAY 56) AND VISIT 8 (DAY 90)

Subjects will be followed for 3 months post first study drug administration. The following assessments will be performed at the follow-up visits:

- Physical exam
- Vital signs
- ECG
- AE and concomitant medication recording
- Partial Mayo score (at Visits 5, 6 and 8)
- Safety laboratory evaluations: hematology, biochemistry, antibodies to bertilimumab
- Blood samples for eosinophil count, serum eotaxin-1ⁱ, hs-CRP^j and ECP
- Blood samples for bertilimumab (PK analysis)
- Calprotectin in fecal samples
- Flexible sigmoidoscopy with biopsies. On Day 56 (or early discontinuation visit), at least 3 tissue samples are required from the same region where the Screening

¹ Visits during the Follow-Up Period have a ±3 day window.

biopsies were obtained. Additional biopsy samples may be obtained at the Investigator's discretion for histological assessment.

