Appendix D Grading of Infusion Reactions

	Grade					
	1	2	3	4		
Signs and	Transient flushing or rash,	Generalized urticaria	Bronchospasm requiring	Anaphylaxis (defined		
symptoms				below); laryngeal/		
	asymptomatic	drug fever >38°C; dyspnea		pharyngeal edema		
	bronchospasm	or reversible	medication; allergy-related	requiring resuscitation;		
		bronchospasm	edema/angioedema;	cardiopulmonary		
				instability requiring		
			symptoms not rapidly	ventilatory support or		
			responsive to interruption	pressors		
			of infusion			
Intervention	None	Infusion held up to 30	Discontinue infusion;	Discontinue infusion;		
		minutes or until symptoms	initiate additional	urgent intervention		
		recede; if symptoms recur	interventions if warranted	indicated		
		upon resuming infusion,	clinically			
		then discontinue infusion				

Anaphylaxis criteria (adopted from the NIAAD/FAAN Clinical Criteria for Anaphylaxis, The Second Symposium on the Definition and Management of Anaphylaxis, Sampson *et al.* 2006): One or both of the following:

- 1. Acute onset of an illness (minutes to several hours) with involvement of the skin, mucosal tissue, or both (e.g., generalized hives, pruritus or flushing, swollen lips-tongue-uvula)

 And at least one of the following:
 - a. Respiratory compromise (e.g., dyspnea, wheeze-bronchospasm, stridor, reduced peak expiratory flow, hypoxemia)
 - b. Reduced blood pressure or associated symptoms of end-organ dysfunction (e.g., hypotonia [collapse], syncope, incontinence)
- 2. Two or more of the following that occur minutes to several hours after exposure to a likely allergen for that patient:
 - a. Involvement of the skin-mucosal tissue (e.g., generalized hives, itch-flush, swollen lipstongue-uvula)
 - b. Respiratory compromise (e.g., dyspnea, wheeze-bronchospasm, stridor, reduced peak expiratory flow, hypoxemia)
 - c. Reduced blood pressure or associated symptoms (e.g., hypotonia [collapse], syncope, incontinence)
 - d. Persistent gastrointestinal symptoms (e.g., crampy abdominal pain, vomiting)

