<sup>6 The pretreatment dosing regimen is as follows: Dexamethasone 10 mg PO 24-18 hours prior to administration of bertilimumab. Acetaminophen 1000 mg PO 1 hour prior to administration of bertilimumab Loratadine 10 mg PO or cetirizine 10 mg PO one hour prior to the administration of bertilimumab. In the event that dexamethasone was not administered previously, then 10 mg dexamethasone IV may be administered one to three hours prior to bertilimumab administration.

At least 3 tissue samples are required from area of active inflammation at Screening. On Day 56 (or early discontinuation visit), at least 3 tissue samples are required from the same region where Screening biopsies were obtained. Additional biopsy samples may be collected at the Investigator's discretion for histological assessment.

<sup>8 Infusion reactions will be monitored for up to 4 hours following study drug administration and graded, as applicable, as appears in Appendix D

<sup>9 Biochemistry will include serum β-hCG at screening.

<sup>10 Blood samples for bertilimumab (PK analysis) will be collected pre-dose, 30 (+15) minutes (immediately post-dose) and 4 hours (± 20 minutes) following initiation of study drug infusion.

<sup>11Partial Mayo Score at Screening will be calculated from the Total Mayo Score.

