## 7.4 Pharmacokinetics (PK) Endpoints

Blood samples will be collected on dosing days (pre-dose and at 30 minutes ( $\pm$  15 minutes) and 4 hours ( $\pm$ 20 minutes) following the initiation of study drug infusion) and at the follow-up visits. The following PK parameters will be calculated:  $C_{max}$ ,  $T_{max}$ ,  $C_{avg}$ ,  $C_{min}$ , and  $t_{1/2}$ . Additional standard and exploratory PK parameters will be calculated if deemed necessary.

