#### **Vital Signs (Body Measurements):**

- Descriptive statistics of weight, blood pressure (Systolic/ Diastolic), pulse rate, temperature and respiratory rate by visit, time point and treatment group.
- For each treatment visit (visits 2, 3 and 4) descriptive statistics of change from pre-dose of the given visit to each time point (15 minutes, 30 minutes, 2 hours and 4 hours post infusion), by treatment group.
- For each treatment visit (visits 2, 3, 4 at 4 hours post infusion time point) and follow up visits (visits 5, 6, 7 and 8) descriptive statistics of change from Screening will be provided by visit and by treatment group.
- Vital signs will also be presented graphically over time by treatment group.

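### The post-infusion PK sample, ECG and vital signs are timed from infusion start, so a held infusion puts them before the end of infusion; the SAP also misstates the PK window and the vital-sign labels (minor)

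*Protocol*

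**What the plan says.** Protocol 5.2 states that "study drug will be administered by IV infusion over 30 minutes". It then lists "Blood samples for bertilimumab (PK analysis) at 30 (+15) minutes (immediately post-infusion) and 4 hours", both counted from the start of infusion, and "ECG at 30 (+15) minutes after initiation of study drug infusion". Vital signs at 30 (+15) minutes use the same clock. Protocol 5.6.3, 5.6.4 and 5.9 repeat the arrangement: all three assessments are counted from the start, and all three are described as falling straight after the infusion.

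Appendix D, in the grade 2 column, has "Infusion held up to 30" minutes, or until symptoms recede, with provision for resuming. No section says what happens to the 30-minute time point after a hold.

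In the SAP, Table 1 footnote 10 has PK samples that "will be collected pre-dose, 30 (+15) minutes (immediately post-dose) and 4 hours", in line with the protocol. SAP 7.4 covers the same samples ("Blood samples will be collected on dosing days (pre-dose and at 30 minutes") but gives the first post-dose window as ±15 minutes. For vital signs, SAP 9.3 summarises change to "each time point (15 minutes, 30 minutes, 2 hours and 4 hours post infusion", whereas Table 1 footnote 4 counts those times from initiation and marks the 15-minute reading as taken during the infusion.

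Protocol 5.9 requires actual PK sampling times to be recorded.

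**The concern.** One time point carries two definitions, which agree only when the infusion runs without a pause. After a hold of more than 15 minutes, a site can sample inside the window while drug is still to be given, or after the infusion but outside the window. It cannot do both.

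A concentration drawn before the infusion ends reflects part of the dose, yet Protocol 8.3.5 and SAP 9.4.3 would summarise it with complete infusions. The single post-dose ECG and the 30-minute vital signs of that subject would likewise be tabulated as post-dose readings. With two post-dose PK samples per infusion, Tmax then falls on the second. Recorded sampling times help only if the end of infusion is also known, and neither document asks for hold, resume or end times.

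The two SAP discrepancies need no infusion reaction to matter: they affect how every subject's results are windowed or labelled.

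**Working it through.** **Inputs.** Infusion length 30 min (Protocol 5.2, 6.2). Window 30 to 45 min after start (Protocol 5.2, 5.6.3, 5.6.4, 5.9; SAP Table 1). Hold h from 0 to 30 min (Appendix D, grade 2). SAP 7.4 PK window 15 to 45 min. Half-life of unbound drug after a single 10 mg/kg dose: 194 h (Protocol 1.3.1).

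**1. The plan's own figure.** End of infusion = 30 + h. With h = 0 it ends at 30 min and the whole 30 to 45 window follows it. The protocol's label reproduces.

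**2. With a hold.** Share of the window before the end = min(h, 15)/15.

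| Hold (min) | Infusion ends (min) | Share of window before end |
|---|---|---|
| 5 | 35 | 5/15 = 33% |
| 10 | 40 | 10/15 = 67% |
| 15 | 45 | 100% (closing minute coincides with the end) |
| 20 | 50 | 100% |
| 30 | 60 | 100% (window closed 15 min earlier) |

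**3. Dose given at sampling, 30-minute hold.** If the infusion stops at minute s, the fraction given at time t is s/30 during the hold and (t − 30)/30 after it resumes.

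| Stop at (min) | Given at 30 min | Given at 45 min |
|---|---|---|
| 5 | 17% | 50% |
| 10 | 33% | 50% |
| 15 | 50% | 50% |
| 20 | 67% | 67% |
| 25 | 83% | 83% |

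A one-compartment constant-rate model (an assumption) with the 194 h half-life gives practically the same relative concentrations at 30 min: 0.166, 0.499 and 0.832 for stops at 5, 15 and 25. The deficit at 30 min therefore runs from 17% to 83% over these stop times. It is 0 when the hold is 15 min or less and the sample is drawn between the end of infusion and 45 min. The 83% belongs to a stop at minute 5; an earlier stop would give more.

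**4. Cmax and Tmax.** Under the same model the 4 h value relative to the end-of-infusion peak is 2^(−3.5/194) = 0.988 without a hold and 2^(−3/194) = 0.989 after a 30-minute hold, about 99% in both cases. That exceeds every held value in step 3, so Tmax is recorded as 4 h, although the infusion ended, and the model peak occurred, at 1 h.

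**5. Group summary.** Up to 42 subjects at 2:1 gives 42 × 2/3 = 28 on active drug. If all 28 are sampled and otherwise have equal concentrations, one affected subject lowers the 30-minute mean at that visit by 50%/28 = 1.8% to 83%/28 = 3.0% (deficits of 50% and 83%).

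**6. SAP 7.4.** In an uninterrupted infusion, 15 of the 30 minutes in the ±15 window (50%) precede the end; under +15 none do. A sample at 15 min would follow 15/30 = 50% of the dose.

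**7. SAP 9.3 against footnote 4.** Both concern the same vital signs. One counts from the start and marks 15 minutes as during the infusion; the other calls all four times post infusion.

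**The case against.** Several points on the other side stand:

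- **Few infusions are affected.** Only grade 2 reactions with a pause and a resumed infusion matter here. The documents give no rate. Protocol 1.3.2 mentions three earlier infusion reactions, one serious, without hold details, and premedication is now given.
- **The hold may be short.** Thirty minutes is a maximum. With 15 minutes or less, a sample after the end still fits the window, and the label makes the intent clear enough that a site may wait.
- **PK is secondary and descriptive.** The synopsis and 8.3.5 already limit the parameters to what the few time points allow, and actual PK sampling times are recorded. The CRF is not among the documents and may already hold infusion start and stop times.

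A reader might infer that the SAP allows all three assessments 15 minutes early. It does not: ±15 appears once, for PK only, while footnotes 4, 5 and 10 give +15. Nor does it send anyone to draw blood at 15 minutes, because sites sample under the protocol. The sign should be confirmed in the signed SAP, since this may be a slip in one character.

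A reader might also infer that the safety readings of reacting subjects are not post-infusion at all. The 2 h and 4 h vital signs follow even a 60-minute end; only the 30-minute reading and the single post-dose ECG are exposed.

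**Conclusion.** The point holds as a minor defect. The 30 (+15) minute time point is counted from infusion start, labelled as after infusion, and not adjusted for a hold that Appendix D allows. Any hold puts minute 30 before the end of infusion; a hold over 15 minutes puts the whole window there. For such an infusion the 30-minute concentration could be 0 to about 83% too low, depending on stop time, hold length and sampling time, and Tmax would be recorded as 4 h.

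The stronger conclusion that Cmax is lost is not supported. Under the one-compartment assumption the 4 h sample is about 99% of peak. A distribution phase could make the error larger, but the documents give no figure for one. The effect on group means is small unless holds are common, and no efficacy analysis is touched.

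The ±15 in SAP 7.4 is a reconciliation error within the SAP and against the protocol. The wording in SAP 9.3 is a labelling error.

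**What to change.** 1. **Protocol 5.2, 5.9, the other PK timing statements and both schedules:** set the post-infusion PK sample at 0 to +15 minutes after the actual end of infusion. For a hold of h minutes that is 30 + h to 45 + h minutes from start, or 60 to 75 for a 30-minute hold.
2. **Record** actual infusion start, hold, resume and end times.
3. **SAP 7.4:** change ±15 to +15 and state the same anchor as the protocol.
4. **SAP 9.3:** relabel the vital-sign times as minutes or hours after start of infusion.
5. **SAP 9.4.3:** leave any sample dated before the end of infusion out of the 30-minute summary, and flag that infusion's Cmax and Tmax as not reliably determined. Exclusion alone is not enough: Tmax would stay at 4 h, taken from the later sample.
6. **ECG and vital signs (Protocol 5.2, 5.6.3, 5.6.4):** reconcile the count from initiation and the post-infusion description with Appendix D.

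The hold rule is a clinical matter and is not questioned. The cost is wording in two documents and, if not already collected, a few time fields. No sample, ECG or visit is added.

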5.4 EARLY DISCONTINUATION STUDY VISIT

An early discontinuation study visit will be performed for subjects who withdraw from the study for the reasons specified in Section 4.5.

All reasons for treatment discontinuation will be documented in the source documents as well as the CRF. Only one reason (the most severe) for early discontinuation should be recorded in the CRF. If one of the reasons for discontinuation is an AE – this should be chosen as the reason. Every effort should be made to follow-up these subjects for resolution of AE.

At this visit, flexible sigmoidoscopy with biopsies will be done in addition to the activities relating to the study period at which time the subject discontinuation visit will be performed. That is, if the subject discontinues during the Treatment period, the visit activities will be similar to those described in Section 5.2; likewise, if the subject discontinues during the Follow-up Period, the visit activities will be similar to those described in Section 5.3. Activities may include (but not limited to): AEs, concomitant medications, laboratory tests, vital signs, and physical examination. Appropriate procedures and evaluations will be completed as deemed necessary by the Investigator.

This visit may be performed on the same day as an originally scheduled visit or could be conducted separately. Data collection at these visits should primarily be guided according to principles to protect subject safety and well-being.

5.5 Unscheduled Visit

An unscheduled visit may be performed at any time during the study at the subject's request or as deemed necessary by the Investigator. The date and reason for the unscheduled visit will be recorded. AE monitoring and concomitant medication recording will be performed by the Investigator. Appropriate procedures and evaluations will be completed as deemed necessary by the Investigator and may include (but not limited to) laboratory tests, vital signs and physical examination.

5.6 SAFETY ASSESSMENTS

Safety assessments will be based on changes from Baseline of AEs (either reported by the subject or observed by the Investigator), concomitant medication use, treatment compliance (e.g., dropouts due to AEs), vital signs, ECG, physical examination and laboratory assessments (hematology, blood chemistry, anti-bertilimumab antibodies).

5.6.1 Adverse Events (AEs)

Adverse events will be assessed throughout the study. Any AE that occurs will be recorded.

Any new AE that occurs between scheduled visits should be brought to the attention of the Investigator and recorded in the subject's medical file and on the appropriate CRF page.

AEs will be coded by Data Management using Medical Dictionary for Regulatory Activities (MedDRA®) version 14.0 or higher (see section 10.4 for more details).

5.6.2 Concomitant Medications

Recording of concomitant medication use will be conducted at all study visits.

5.6.3 Vital Signs

Vital signs will be measured at all study visits. On dosing days, vital signs will be measured pre-dose and at 15 minutes (during infusion), 30 (+15) minutes (immediately post infusion), $2 \text{ hr} (\pm 20 \text{ minutes})$ and $4 \text{ hr} (\pm 20 \text{ minutes})$ following initiation of study drug administration.

Vital signs will include blood pressure, pulse rate, oral temperature and respiration rate after at least 5 minutes rest as per standard practice at the investigational site. Significant findings noticed after the start of study drug, which meet the definition of an AE must be recorded on the AE CRF module.

5.6.4 Electrocardiogram

ECG will be performed at all study visits. On dosing days, ECG will be performed pre-dose, and at 30 minutes (+ 15 minutes) following initiation of study drug administration (immediately post-infusion). The subject should rest for at least 10 minutes before measurement is taken.

The ECG will be evaluated by the Investigator (signed and dated) and the printout should be kept in the source documentation file. When potentially clinically significant findings are detected by the site Investigator, a cardiologist should be consulted for a definitive interpretation and treatment administered based on medical need. All communications and diagnoses should be filed in the source documentation file. The Investigator/local cardiologist is responsible to determine whether the ECG findings are of clinical significance. All abnormalities will be closely monitored until stabilized or resolved.

5.6.5 Physical Examination

Physical examination will be conducted at all study visits. On dosing days, physical examination will be performed pre-dose. Height will be recorded at Visit 1 (screening). Physical examination will include weight measurements, assessment of head, lungs, cardiovascular system, abdomen, musculoskeletal system, skin, lymph nodes, central nervous system and, where appropriate, other body systems as indicated in the study schedule.

Information about the physical examination must be present in the source documentation at the study site. Significant findings that are present prior to the start of study drug must be included in the Relevant Medical History/Current Medical Conditions CRF. Significant findings made after the start of study drug, which meet the definition of an AE must be recorded on the AE CRF.

5.6.6 Infusion Reactions

Infusion reactions to monoclonal antibody administration are not uncommon and are typically mild to moderate in intensity. They can develop during the infusion or several hours thereafter, and, are most commonly associated with a complex of chills, fever, nausea, asthenia, headache, skin rash or pruritus. However, infusion reactions in a small percentage of patients, may also present with a variety of signs and symptoms of severe hypersensitivity characterized by the acute onset of bronchospasm, hypotension, urticaria and/or cardiac arrest. Therefore, all subjects in the study will be pre-medicated with a prophylactic regimen prior to study treatment on each of the dosing days (Days 0, 14 and 28) to prevent potential infusion reactions and will be closely monitored for up to 4 hours post-infusion.

5.6.7 Safety Laboratory Assessments

Clinical laboratory assessments will be performed by a central laboratory. Investigators at each site will review these laboratory data for safety considerations. Hematology and biochemistry will be conducted at all study visits. Screen for active/latent mycobacterium tuberculosis (TB) infection and *Clostridium difficile* toxin stool assay will be conducted at screening only. Anti-bertilimumab antibodies will be evaluated from Day 0 until the end of the study. Pregnancy test for women of childbearing potential will be conducted at Screening (serum) and before each study drug infusion (urine).

Safety laboratory sampling will be performed as follows by a central laboratory:

Evaluations	Parameters
Hematology	Hematocrit, hemoglobin, platelet count, red blood cell count, reticulocytes, white blood cell count with differential count
Biochemistry	Alanine aminotransferase, alkaline phosphatase, α-amylase, aspartate aminotransferase, calcium, cholesterol, creatinine, gamma-glutamyl transferase, glucose, potassium, sodium, total bilirubin, triglycerides, urea/BUN
Immunology*	Anti-bertilimumab antibodies
Pregnancy test	Serum β-hCG pregnancy test at Screening Urine β-hCG on dosing days (pre-dose)
	Urine B-hCG on dosing days (pre-dose)

The volume of blood to be drawn for each subject and processing and storage of samples are detailed in the Laboratory Manual.

All laboratory tests with values that became abnormal and are considered clinically significant after drug administration will be repeated as clinically indicated until the values return to normal, or until the etiology has been determined and the condition considered stable. Abnormal laboratory test results that are considered to be clinically important by the Investigator will be reported as an AE in the AE CRF. A laboratory abnormality will not be considered an AE unless:

- Intervention is required
- Changes in dose are required (decrease, discontinued, interrupted)
- Other treatment/therapy is required
- It is associated with other diagnoses.

Laboratory results will be reported to the Investigator who will review abnormal laboratory findings for clinical significance. The Investigator will note any laboratory test results of clinical concern, or values that were outside normal ranges and provide details of the relationship to investigational product and the action taken. If a change in a laboratory value represents a medical condition, the medical condition will be listed in the AE CRF page. If no correlation is possible, the direction of change (increase or decrease) in addition to the actual value will be recorded.

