7. SAFETY AND PHARMACOVIGILANCE

7.1 ADVERSE EVENT

An adverse event (AE) is any adverse change from the subject's baseline condition, whether or not considered investigational product related. This includes any subjective signs, symptoms or diagnosis, clinical significant deviation from baseline laboratory values or vital signs, or worsening (more severe, more frequent or increased in duration during the investigational product treatment) of the concomitant disease present at baseline visit (after initiation of investigational product treatment). Stable chronic conditions that are present prior to study entry and do not worsen during the study will not be considered AEs. Disease-related adverse events will not be considered AEs only if they worsen beyond what would be

expected in the normal progression of the disease. In all cases, the etiology should, as much as possible, be identified and the Sponsor notified.

An abnormal result of diagnostic procedures including abnormal laboratory or vital sign findings will be considered an AE if it:

- Results in subject's withdrawal by the Investigator
- Is associated with clinical signs or symptoms
- Is considered by the physician to be of clinical significance.

Adverse events reported by the subject or observed by the Investigator will be individually listed on an AE form in the CRF as follows: the specific event or condition, whether the event was present pre-study, the dates and times of occurrence, duration, severity, relationship to study medication, specific countermeasures and outcome.

The intensity or severity of the AE will be characterized as:

• Mild: Transient or mild discomfort; no limitation in activity; no medical

intervention/therapy required.

• Moderate: Mild to moderate limitation in activity - some assistance may be

needed; no or minimal medical intervention/therapy required.

• Severe: Marked limitation in activity, some assistance usually required;

medical intervention/therapy required; hospitalization possible.

The Investigator will document in his/her opinion the relationship of the AE to the investigational product (study medication) using the following criteria:

Category	Definition	
Unrelated	Clearly due only to extraneous causes, and does not meet criteria listed under possible or probable.	

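### Protocol sections 5.6.7 and 7.1 set conflicting rules for when a laboratory abnormality is an AE, so a clinically significant result that is only monitored can be recorded either way

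*Protocol*

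**What the plan says.** Both rules are in the current body of the Protocol.

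- **Section 5.6.7, inclusive sentence:** "Abnormal laboratory test results that are considered to be clinically important by the Investigator will be reported as an AE in the AE CRF".
- **Section 5.6.7, the very next sentence:** "A laboratory abnormality will not be considered an AE unless" one of four conditions is met: "Intervention is required"; a change of dose is needed; "Other treatment/therapy is required"; or "It is associated with other diagnoses". Clinical significance is not among them, and neither are signs or symptoms.
- **Section 7.1:** an abnormal diagnostic result, "including abnormal laboratory or vital sign findings will be considered an AE if it" leads the Investigator to withdraw the subject, comes with signs or symptoms, or "Is considered by the physician to be of clinical significance". The general AE definition in the same section also takes in a clinically significant departure from baseline laboratory values.

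No statement in the Protocol ranks these rules. The SAP does not settle the matter. Its section 8 covers coding, and section 9.3 tabulates TEAEs and summarises laboratory results. Neither gives a criterion for when a laboratory result becomes an AE.

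**The concern.** The rule in 7.1 is a sufficient condition: clinical significance alone makes the result an AE. The list in 5.6.7 is a necessary condition: without one of its four items the result is not an AE. A result judged clinically significant and then only repeated and watched satisfies the first and fails the second. The situation is foreseeable, because 5.6.7 itself has clinically significant post-dose abnormalities repeated until they normalise or are explained and stable.

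Safety is part of the primary objective (Protocol 2.1). TEAE incidence by arm, with worst severity and worst relationship, is a main safety output (Protocol 8.3.7.1; SAP 9.3). The wording will be applied at about 10-12 sites, possibly more, so two readings would produce AE counts that depend partly on the site's interpretation.

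**Working it through.** The plan gives no figure to reproduce here. The check is a logical comparison, followed by the size of one reclassification.

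**1. The rules as conditions**
- Section 7.1: AE if W or S or C (withdrawal, signs or symptoms, clinical significance).
- Section 5.6.7 list: not an AE unless I or D or T or X (intervention, dose change, other therapy, other diagnosis).

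**2. Cases in conflict**
- Seven yes/no items give 2^7 = 128 combinations.
- A conflict needs at least one of W, S, C (2^3 − 1 = 7 ways) and none of I, D, T, X (1 way), so 7 × 1 = 7 combinations conflict.
- If withdrawal is taken to imply discontinuing the dose, combinations with W present and D absent drop out. That leaves 64 + 32 = 96, and the conflicts fall to 2^2 − 1 = 3: significant only, symptomatic only, or both.
- In 2 of these 3 the result is clinically significant, so the sentence preceding the list also calls it an AE and 5.6.7 contradicts itself. In the third (symptoms only) the conflict is between 7.1 and the list.

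These are counts of logical cases, not expected frequencies.

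**3. Which cases matter in practice**
- Section 7.1 already counts a symptom that is an adverse change from baseline as an AE in its own right.
- The last paragraph of 5.6.7 requires a medical condition represented by a laboratory change to be listed on the AE page.
- A symptomatic subject would therefore normally have an AE on record anyway. At most a separate laboratory term is lost.
- The main remaining case is a clinically significant result with no symptoms, managed only by observation.

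**4. Size of one reclassification**
- Protocol 8.3.7.1 defines crude incidence as subjects with the event divided by subjects exposed, and counts a subject once per preferred term.
- Assume all 42 subjects are dosed at exactly 2:1: 42 × 2/3 = 28 on bertilimumab and 42 × 1/3 = 14 on placebo.
- One subject newly counted under a term: 1/28 = 3.6 percentage points, or 1/14 = 7.1 percentage points.
- The step is zero for a preferred term the subject already has, and zero for the any-TEAE rate if the subject has any other TEAE.
- The sample size is given as a maximum. With fewer subjects dosed, each step (1 divided by the arm size) is larger.

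The documents give no expected frequency of such results, so the total effect cannot be computed.

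**The case against.** **The list may only refine the sentence before it.** On that reading 5.6.7 is consistent within itself. The conflict with 7.1 remains, because 7.1 needs nothing beyond clinical significance. The list also sits awkwardly with the severity scale in 7.1, which describes a mild event as needing no medical intervention or therapy, whereas three of the four list items require an intervention, dose change or therapy.

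**Nothing is lost from the data.** This largely stands. Section 5.6.7 has the Investigator note results of clinical concern or out of range, with relationship and action taken. Protocol 8.3.7.2 summarises treatment-emergent laboratory abnormalities by arm, and SAP 9.3 adds normality frequencies and shifts. An imbalance in transaminases, for example, could be seen there however AEs are classified. What those outputs do not carry is the AE tabulation by maximal severity and relationship, which SAP 9.3 plans for AEs only.

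**SAE reporting might suffer too.** A reader might infer that the narrower list removes events from SAE reporting. The documents do not support this. Seriousness in Protocol 7.2 rests on outcomes such as death, hospitalisation or disability, or on a possible need for intervention to prevent them. A result that is only monitored would ordinarily meet none of these, and one that did would ordinarily meet a list item as well.

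**Every reclassified abnormality might seem to shift the rate.** It does not, because incidence counts subjects and not abnormalities.

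**Conclusion.** The inconsistency is real and stands in operative text. Section 7.1 and the inclusive sentence in 5.6.7 make a clinically significant result an AE, the list that follows says it is not one unless a further condition is met, and no rule of precedence is given. The consequence is limited to possible site-dependent recording, mainly of asymptomatic, clinically significant abnormalities that are only monitored, and hence to TEAE incidence and its severity and relationship tables.

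The step of 3.6 or 7.1 points applies per newly counted subject and rests on the assumption of 28 and 14 subjects dosed. How many subjects would be affected is unknown. This is a minor point, worth correcting because correction is cheap and safety is part of the primary objective. It is not evidence that laboratory signals would be missed.

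**What to change.** Reconcile the passages so that one AE criterion applies to laboratory results. The simplest way is to replace the restrictive list in 5.6.7 with a cross-reference to 7.1, since 7.1 is the AE definition section and the sentence before the list already agrees with it. The choice of criterion is the sponsor's. If the narrower list is preferred, 7.1 and the preceding sentence in 5.6.7 need to be changed to match.

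Before database lock, check results that the Investigator noted as being of clinical concern for a matching AE entry. This can be done only as far as that judgement is recorded. The SAP has clinical-significance categories for physical examination and ECG but none for laboratory results, and Protocol 8.3.7.2 flags laboratory values only as high or low.

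The cost is a protocol clarification, one data check and possibly slightly more AEs recorded.
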